1 TRIAL SUMMARY

World Health Organization Registration Data Set

Title

High flow nasal oxygen during conscious sedation in the cardiac catheterisation laboratory: A randomized controlled trial

Primary registry and trial identifying number	ClinicalTrials.gov NCT03858257
Secondary identifying numbers	CAPCR 18-6343
Sources of monetary or material support	This study will be fully supported by funds received by the PI, [name], for his appointment as Chair of Cardiovascular Nursing Research at PMCC. This includes all work undertaken by the Research Coordinator and purchasing of equipment and consumables for the HFNO and TcCO ₂ monitoring devices.
Primary sponsor	Investigator-sponsored trial
Secondary sponsors (if any)	n/a
Central contact	[name], PhD RBC Chair in Cardiovascular Nursing Research Peter Munk Cardiac Centre Toronto General Hospital University Health Network Assistant [name] Faculty of Nursing, University of Toronto Toronto General Hospital Heart & Circulation Admin 4NU - 476 [name] [contact] [contact] (mailto:[contact])
Study officials/Investigators	[name], PhD Study Principal Investigator
Brief title	High flow nasal oxygen during sedation
Acronym	n/a

Countries of recruitment	Canada
Condition(s) or focus of study	High flow nasal oxygen (HFNO) during procedural sedation.
Interventions	
High flow nasal oxygen	
Intervention type: Device
 
Intervention name: High flow nasal oxygen
 
Intervention description: The Optiflow device (Fisher and Paykel Healthcare, Auckland, New Zealand) will be used. The gas temperature will commence at the 'High' setting (ranges 30-32° Celsius) and titrated downwards if the patient complains of irritation. The gas flow rate will commence at 30 liters per minute prior to sedation administration and be titrated up to 70 liters per minute as tolerated by the patient after sedation has been administered. The fraction of oxygen in the gas will be commenced at 50% (same as that delivered from 6 liters per minute via facemask) and can be titrated upward according to patient requirements (i.e. increased if there is evidence of hypoventilation, airway obstruction or inadequate oxygenation).

Facemask oxygen supplementation (usual care)	
Intervention type: Device
 
Intervention name: Facemask oxygen supplementation
 
Intervention description:

Supplemental oxygen through a facemask with the flow rate chosen by the clinician responsible for sedation as per their standard practice. The oxygen flow rate is typically commenced at 6 liters per minute and can be titrated up to 15 liters per minute.

Key eligibility criteria

Age eligibility: 16 years or older

Sex eligibility: Both

Accepts healthy volunteers: No

Inclusion criteria:

1. Adults undergoing an elective cardiac implantable electronic device procedure in the Peter Munk Cardiac Centre Cardiac Cath Labs with conscious sedation administered by an Anesthesia Assistant (de novo and replacement/revision procedures).

Exclusion criteria:

1. Under 16 years of age.
2. Underlying condition requiring chronic oxygen supplementation.
3. Diagnosed respiratory condition with confirmed current hypercapnia.
4. Pre-existing untreated pneumothorax.
5. Transesophageal echocardiography planned for the procedure.
6. Active nasal bleeding.
7. Complete nasal obstruction.
8. Recent upper airway surgery or

base of skull fracture.

9. Previous participation in the study.

Study design	
Study type: Interventional trial Allocation: Randomized Intervention model: Parallel group Primary purpose: Health Services Research Phase: n/a

Masking	Outcome assessors
Date of enrollment	June 2019 (anticipated)
Target sample size	150
Recruitment status	Not yet recruiting
Primary outcomes	
Outcome: Peak transcutaneous carbon dioxide (TcCO₂) concentration
 
Timeframe: From the time between first sedative medication administration to the end of the procedure. Estimated duration of procedures is 30 minutes to 120 minutes.
 
Description: Continuous measurements will be recorded using the Sentec Digital Monitoring System with VSign 2 sensor.

Secondary outcomes	
Outcome: Mean transcutaneous carbon dioxide concentration
 
Timeframe: From the time between first sedative medication administration to the end of the procedure. Estimated duration of procedures is 30 minutes to 120 minutes.

Description: Continuous measurements will be recorded using the Sentec Digital Monitoring with VSign 2 sensor

Outcome: Trajectory of transcutaneous carbon dioxide as a function of time

Timeframe: From the time between first sedative medication administration to the end of the procedure. Estimated duration of procedures is 30 minutes to 120 minutes.

Description: Continuous measurements will be recorded using the Sentec Digital Monitoring with VSign 2 sensor

Outcome: Area under SpO₂ 90% desaturation curve

Timeframe: From the time between first sedative medication administration to the end of the procedure. Estimated duration of procedures is 30 minutes to 120 minutes.

Description: Difference between the threshold (90%) and actual oxygen saturation (SpO₂) summed every second during which oxygen saturation was below threshold.

Outcome: Adverse sedation events

Timeframe: From the time between first sedative medication

administration to the end of the procedure. Estimated duration of procedures is 30 minutes to 120 minutes.

Description: The Anaesthesia Assistant will be asked to complete the Tracking and reporting outcomes of procedural sedation (TROOPS) tool at the end of procedures. Completion of the tool requires identification and description of the adverse event, the intervention, the outcome and the overall severity of the adverse event.

Outcome: Patient satisfaction with sedation

Timeframe: After the participant has reached phase 2 post-anesthetic recovery. Estimated to be 30 minutes after procedure has finished.

Description: Iowa Satisfaction with Anesthesia Scale

Outcome: Costs associated with oxygen delivery

Timeframe: From the time between first sedative medication administration to the end of the procedure. Estimated duration of procedures is 30 minutes to 120 minutes.

Description: Anesthesia Assistants will document devices used for supplemental oxygen delivery and airway management

in both groups as per their usual practice in the anesthesia monitoring system.

Outcome: Anesthesia Assistant rating of difficulty maintaining oxygenation status

Timeframe: To be completed as soon as possible after the end of the procedure (within about 5 minutes).

Description: 6-level rating scale from “extremely difficult” to “extremely easy”

Outcome: Anesthesia Assistant rating of difficulty using oxygen delivery device

Timeframe: To be completed as soon as possible after the end of the procedure (within about 5 minutes)

Description: 6-level rating scale from “extremely difficult” to “extremely easy”

Outcome: Patient comfort of oxygen delivery

Timeframe: After the participant has reached phase 2 post-anesthetic recovery. Estimated to be 30 minutes after procedure has finished.

Description: 6-level rating scale from “maximal discomfort” to “maximal comfort”

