The Optiflow device (Fisher and Paykel Healthcare, Auckland, New Zealand), heated breathing tube and chamber, and nasal cannula will be used. This system is a humidifier with an integrated flow generator, able to humidify respiratory gases and deliver them down a heated breathing tube and through the nasal cannula interface. The gas temperature will commence at the ‘High’ setting (ranges 30-32° Celsius) and titrated downwards if the patient complains of irritation. The gas flow rate will commence at 30 liters per minute prior to sedation administration and be titrated up to 70 liters per minute as tolerated by the patient after sedation has been administered. The fraction of oxygen in the gas will be commenced at 50% (same as that delivered from 6 liters per minute via facemask) and can be titrated upward according to patient requirements (i.e. increased if there is evidence of hypoventilation, airway obstruction or inadequate oxygenation, decreased during use of diathermy). Anesthesia Assistants at the site will be provided with training in the use of this mode of oxygen delivery prior to study commencement.

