4. Adverse sedation events: Adverse effects of delivering gas at a high flow rate through the nasal passages will be assessed. These include nose bleeding arising from damage to the

mucosal surface and pressure injury to skin from the device. The RA will inspect intervention group participants' skin integrity around the nasal region at the end of procedures to assess for these potentially anticipated as well as unanticipated adverse effects.

5. Patient satisfaction with sedation: The Iowa Satisfaction with Anesthesia Scale (ISAS) will be used to measure patient satisfaction with the anesthetic used during the procedure performed.
6. Costs associated with oxygen delivery: The amount of consumable equipment required for oxygen delivery used during procedures and throughout the recovery period will be measured using a data collection form specifically designed for this study.
7. Patient comfort of oxygen delivery: Participants will be asked to rate at the end of procedures their perceived overall comfort with the oxygen delivery device used during the procedure using a 6-level ratings scale.
8. Anesthesia Assistant rating of difficulty maintaining oxygenation status.
9. Anesthesia Assistant rating of difficulty using oxygen delivery device.

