3.5 Participant timeline

Data for this study will be collected by the RA and entered into an electronic data platform supported by REDCap™ (Research Electronic Data Capture Vanderbilt University, Nashville, TN, USA) at three time points: (T1) at baseline (prior to procedures); (T2) during the procedure; and (T3) on hospital discharge.

After receiving participant consent, demographic information and eligibility to participate will be confirmed at T1. Transcutaneous carbon dioxide (TcCO₂) monitoring and pulse oximetry will be measured continuously at T2. Adverse sedation events, patient comfort with sedation, difficulty maintaining oxygen saturation and using the device, and cost associated with the oxygen delivery device will be assessed at T3. Patient satisfaction with sedation will also be assessed at this time using the Iowa Satisfaction with Anesthesia Scale (ISAS) through REDCap™.

	During Pre-procedure procedure	Post- procedure
--	---	----------------------------

TIMEPOINT	T1	T2	T3
ENROLLMENT:	X		
Eligibility screen	X		
Informed consent	X		
Allocation	X		
INTERVENTIONS:			
Facemask oxygen supplementation		X	
High flow nasal oxygen		X	
ASSESSMENTS:			
Demographic information and medical history	X		
Peak TcCO ₂ concentration		X	
Mean TcCO ₂		X	
Area under the curve of oxygen desaturation		X	
Adverse sedation events			X
Patient satisfaction with sedation			X
Costs associated with oxygen delivery			X
Anesthesia Assistant rating of difficulty maintaining the patient's oxygenation			X

status

Anesthesia Assistant rating of difficulty using oxygen delivery device	X
Patient comfort of oxygen delivery	X

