3.10 Data collection

3.10.1 Trial procedures and evaluations

Instruments used to measure outcomes

Transcutaneous carbon dioxide concentrations: PI [name] will provide training to the RA in use of the transcutaneous carbon dioxide monitoring device and other data collection procedures. The RA will attach the Sentec VSign 2 sensor to the participant's forehead using a multi-site attachment ring. Once the Sentec Digital Monitoring System displays a stabilized TcCO₂ level, the monitor will be covered with a drape so that it is not visible to research staff or clinicians during the procedure. The monitor will not be used by the clinicians to guide treatment. Data will be downloaded to a computer using the USB port on the monitor. TcCO₂ monitoring provides continuous, accurate (mean bias within 2 mmHg) and precise (95% limits of agreement within 6 mmHg) estimates of arterial CO₂ (PaCO₂) in sedated patients.¹⁴

Pulse oximetry: Percentage of hemoglobin saturated with oxygen (SpO₂) will be measured continuously throughout procedures as part of routine clinical practice through the anaesthetic machine. We will access the DREAM (Drug Reconciliation and Electronic Anesthesia Monitoring) system to download this data. Unreliable SpO₂ measurements will be filtered out if a pulse rate is not detectable.

Tracking and reporting outcomes of procedural sedation tool.²³ This tool was developed, using a consensus process, by members of a multidisciplinary society who had demonstrated capacity, dedication and competence in research and/or clinical experience in procedural sedation. Completion of the tool requires identification and description

of the adverse event, the intervention, the outcome and the overall severity of the adverse event. The Anaesthesia Assistant will be asked to complete this tool at the end of procedures. It takes approximately 2 minutes to complete.

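### Adverse sedation events are counted and captured only up to the end of the procedure, so recovery-period events and late nasal or skin effects fall outside the between-arm comparison

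*Combined protocol and SAP*

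**What the plan says.** In section 1 (Trial Summary, Secondary outcomes), the adverse sedation event entry opens its window with "Timeframe: From the time between first sedative medication" and continues "administration to the end of the procedure. Estimated duration of procedures is 30 minutes to 120 minutes". It names the TROOPS tool as the instrument. Section 3.10.1 fixes when that tool is filled in: "The Anaesthesia Assistant will be asked to complete this tool at the end of procedures".

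Section 3.4, secondary outcome 4, describes the same outcome through device effects, namely nose bleeding and pressure injury to skin. The Research Assistant is to inspect "skin integrity around the nasal region at the end of procedures", in the intervention group. Section 3.10.1 repeats this under Adverse effects.

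Section 3.5 sets three data collection points and defines T3 in its text as hospital discharge; the schedule table heads the same column as post-procedure. The outcomes it places at T3 begin with "Adverse sedation events, patient comfort with sedation, difficulty maintaining oxygen saturation and using the device".

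Three other statements bear on timing:
- Section 3.3.1, on the start of high flow nasal oxygen (HFNO): "The gas flow rate will commence at 30 liters per minute prior to sedation administration".
- Section 1, on when satisfaction and comfort are asked: "After the participant has reached phase 2 post-anesthetic recovery. Estimated to be 30 minutes after procedure has finished".
- Section 3.4, secondary outcome 6 (costs), on consumable equipment "used during procedures and throughout the recovery period will be measured".

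Section 3.14 separately requires any adverse event, related or not, to be reported to the Nurse Manager, the Principal Investigator and the Research Ethics Board. It states no time window.

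**The concern.** The window and both capture methods stop when the procedure stops. The plan itself places a recovery phase after that point and schedules adverse event assessment at discharge, yet it gives nobody the task of finding events from the interval and assigning them to the outcome. A respiratory event in recovery, or a pressure mark or nosebleed that shows itself later, would not enter the comparison between arms.

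Section 2.1 says that the potential disadvantages of HFNO should be evaluated. Sections 3.13.1 and 3.13.2 provide no monitoring committee and no interim analysis, and the transcutaneous CO₂ and SpO₂ outcomes also end with the procedure. This secondary outcome is therefore the only planned between-arm comparison of adverse events. A statement of no excess harm would rest on the in-procedure period, and a reader could take it to cover the whole episode of care.

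**Working it through.** This is a question of timing, and no sample-size figure depends on it. The plan's 130 participants are for peak transcutaneous CO₂. With a 4 mmHg difference, SD 7 mmHg, two-sided 5% and 90% power, 2 × (1.960 + 1.282)² × 7² / 4² = 64.4, or 65 per arm and 130 in total, so that figure reproduces and is unaffected. The adverse event outcome has no size or power figure of its own.

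**Step 1: set the times side by side.**

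| Item | Time | Place |
|---|---|---|
| HFNO begins | Before sedation, lead time not given | 3.3.1 |
| Event window opens | First sedative | 1 |
| Event window closes | End of procedure | 1 |
| TROOPS completed | End of procedure | 1, 3.10.1 |
| Nasal and skin inspection, HFNO arm | End of procedure | 3.4, 3.10.1 |
| Satisfaction and comfort asked | Phase 2 recovery, about 30 min later | 1 |
| Adverse events assessed (T3) | Hospital discharge (text) or post-procedure (table) | 3.5 |
| Safety reporting | No window | 3.14 |

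**Step 2: the closing end.** Events after the procedure fall outside the window. The two named instruments have already been completed, so they could not record such events even if the window were longer. T3 comes later, but no instrument is named for finding recovery events there.

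**Step 3: the opening end.** A sedation event cannot precede the first sedative, so nothing is lost for TROOPS. A device effect can precede it. The inspection will find any nasal or skin effect still visible, whenever it began. What can be lost is a transient effect, such as a nosebleed, that begins with the device and resolves before the inspection.

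**Step 4: scale in time.** Assume that procedure length D runs from first sedative to end of procedure; the documents do not say so. The share of the time from first sedative to phase 2 that lies outside the window is 30 / (D + 30):

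- D = 30 min: 30/60 = 50%
- D = 60 min: 30/90 = 33%
- D = 90 min: 30/120 = 25%
- D = 120 min: 30/150 = 20%

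The pre-sedation HFNO time and the time from phase 2 to discharge have no stated length and cannot be added.

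**The case against.** The best defence is that the window matches the intervention. Section 3.5 places both oxygen devices at T2 only, and the physiological outcomes use the same window. Counting events over the period of randomized exposure is a legitimate choice. This stands, and it is why the procedure-only count should be kept. It does not explain why adverse events are scheduled for assessment at discharge without a means of collecting later ones.

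Several stronger readings are tempting, and the documents do not support them:

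- *The T3 schedule contradicts the window.* A window says which events count; an assessment time says when they are recorded. Recording in-procedure events afterwards satisfies both. The real inconsistency is narrower: discharge in the text of section 3.5 against end of procedure for TROOPS and the inspection.
- *The window is equally wrong at its start.* Step 3 shows that little is lost there.
- *Recovery events have no route at all.* Section 3.14 has no time limit. It is, however, passive reporting of single cases, with no systematic collection and no comparison by arm.
- *Patients remain sedated or on the assigned device in recovery.* The documents do not say this. The reference to the recovery period in section 3.4 concerns counting consumables for costs, and the Trial Summary ends even the cost window with the procedure.
- *Between 20% and 50% of events are missed.* The figure is clock time, and the 30 minutes is an estimate used to time questionnaires, not a stated risk period.
- *The gap favours HFNO.* A lost transient device effect would favour HFNO, but inspecting the nasal region in the HFNO arm only pushes detection the other way.

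**Conclusion.** The point holds in a limited form. As written, the between-arm adverse event outcome leaves out sedation events in recovery and nasal or skin effects that appear after the procedure, and T3 is not defined consistently. The pre-sedation gap is minor.

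The 20% to 50% figure describes only the time left uncovered, under the assumption in Step 4. The documents give no event rate for recovery or for the pre-sedation period, so neither the number of events missed nor the direction of any bias can be derived.

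The primary outcome and the sample size are untouched. This is a secondary safety outcome and the correction is cheap, so it is worth making, but it does not put the trial's main conclusion at risk. If the outcome is left as it is, any safety statement should be limited to the period from first sedative to end of procedure.

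**What to change.** 1. Define T3 once and use that definition in the text and table of section 3.5.
2. In sections 1, 3.4, 3.5 and 3.10.1, state the event window separately from the time at which events are recorded.
3. Keep the TROOPS count from first sedative to end of procedure as registered.
4. Add a recovery-period count from end of procedure to the existing T3 contact. The Research Assistant collects it the same way in both arms, primarily from the recovery record.
5. Record device effects from application of the device onward, so that a transient effect before sedation is noted when it occurs.
6. Report procedural events, recovery events and any pre-sedation device effects separately by arm.

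The cost is protocol wording, an added item on the T3 form and a few minutes at a contact that already takes place for satisfaction and comfort. A few more events will need recording and reporting. Any events reported by patients will be unblinded, since section 3.9.1 says participants and personnel cannot be masked; this is why the recovery record should be the main source. Separate reporting keeps the registered count intact.

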2 INTRODUCTION

2.1 Background and rationale

High flow nasal oxygen (HFNO) is increasingly regarded as a promising technology for oxygen delivery in critical care and anesthetic management.¹ It permits flows of heated, humidified gas to be delivered to the lungs via nasal prongs at up to 70 liters per minute. Delivering oxygen at such high flow rates into the lungs has multiple physiological effects that may better support the vulnerable breathing state of patients during procedural sedation. For example, it permits more precise titration of the amount of oxygen being administered to the patient because the flow rate exceeds normal inspiratory volumes (about 30 liters per minute). HFNO also increases pressure in the upper airways (which may reduce airway obstruction) and decreases the space within the airways where gas is not able to come in contact with blood and exchange oxygen for carbon dioxide to be exhaled.

In anticipation that the physiological effects of delivering HFNO may lead to improved clinical outcomes, multiple large-scale randomized controlled trials were conducted to test this technology across a variety of critical care populations including acute respiratory failure²⁻⁴ and post cardiac surgery.⁵ There have also been multiple trials testing the efficacy of integrating HFNO into anesthetic management plans, including for pre-oxygenation prior to, and apneic oxygenation at, anesthetic induction.^{6,7}

There is heightened interest in investigating the effects of HFNO therapy for procedural sedation at present. Three small randomized controlled trials of HFNO during procedural sedation have been published in the last year, with a further 5 trials registered at clinicaltrials.gov. One study randomized 60 participants undergoing bronchoscopy to receive HFNO at 50 liters per minute with 100% oxygen or to receive oxygen at 10-15 liters per minute through a facemask.⁸ There was no difference observed between the treatment groups for the primary outcome, which was the proportion of patients who experienced oxygen desaturation (defined as SpO₂ 90%). Another study randomized 59 morbidly obese patients undergoing endoscopy to receive a fraction of inspired oxygen concentration of 0.36 either via HFNO at a flow rate of 60 liters per minute or via nasal cannula at 4

liters per minute.⁹ Again, there was no difference in the primary outcome of oxygen desaturation (SpO₂ 90%). The third study randomized 30 participants undergoing dental sedation into three groups to receive a fraction of inspired oxygen concentration of 0.4 either via HFNO at a flow rate of 50 liters per minute, via HFNO at a flow rate of 30 liters per minute or via nasal cannula at 5 liters per minute.¹⁰ Participants randomized to the HFNO groups had higher nadir blood oxygen levels recorded than the low flow oxygen group. Overall, the results from the studies published to date indicate that using HFNO may not result in a substantially improved oxygenation status. However, only 159 participants in total were enrolled in these studies. Therefore, further research is required to elucidate the effects of this technology on respiratory function of sedated patients.

For example, it is important to evaluate the effects of this new technology in each of the diverse contexts in which procedural sedation is used. None of the previous or in-progress clinical trials have enrolled patients undergoing cardiology procedures. In this regard, it is important to note that oxygen desaturation occurs rarely in the context of the common clinical situation where conscious sedation is administered with prophylactic oxygen supplementation at flow rates between 6-10 liters per minute through a face mask during procedures performed in the cardiac catheterisation laboratory.¹¹ Results from trials of HFNO during sedation conducted in other clinical settings, such as bronchoscopy and gastrointestinal endoscopy, where desaturation occurs more often, can therefore not be directly generalised to the cardiology context.

It is also essential that all of the potentially beneficial effects of HFNO on respiratory function during sedation are comprehensively evaluated. Although oxygen desaturation is not common during cardiology procedures, patients commonly have raised arterial carbon dioxide levels, indicating that hypoventilation does occur. One of the proposed physiological effects of HFNO is that it facilitates active gas exchange during times of hypoventilation due to the highly turbulent supraglottic flow vortices.¹²

The effects of the potential disadvantages of using HFNO during sedation should also be evaluated. It is possible that potential gains arising from delivering oxygen supplementation through the HFNO device may be offset by reduced ability to monitor ventilation from capnography waveforms when it is being used. Capnography

waveforms have not been validated for accuracy during HFNO therapy due to exhaled carbon dioxide being “washed out” by the high flows of gas.

The impact of using high flow nasal oxygen delivery systems routinely for conscious sedation on departmental costs is also unclear. Evidence from a pre-test post-test study of switching to routine use of HFNO in a critical care unit actually reduced departmental costs.¹³

In summary, although promising, further high-quality studies examining the effects of using HFNO during procedural sedation are required to inform decision-making regarding implementation of this new technology into practice. The 2018 guidelines from the American Society of Anesthesiology stated that there is insufficient evidence regarding which methods of supplemental oxygen administration (e.g., nasal cannula, face mask, or specialized devices such as HFNO) are more effective. This trial will address this limitation in the evidence base specifically in regard to the efficacy of using HFNO during conscious sedation in the cardiac catheterisation laboratory. Results from our study will provide clinical evidence regarding the effects of HFNO on ventilation in sedated patients.

